8.1.3. Virology Assessments

Respiratory tract samples

SARS-CoV-2 positivity should be documented based on local testing on any specimen, by RT-PCR any time before randomization. This might require a local test using a NP swab obtained at screening.

In addition, nasopharyngeal swabs will be collected for central testing. An NP swab will be used to collect secretions from patients to explore quantification of viral load of SARS-CoV-2 virus. At baseline, the presence of other respiratory pathogens, using multiplex PCR, will also be tested. Furthermore, sequencing might be performed upon request of the virologist to determine mutations in the viral genome.

For participant who are intubated, endotracheal samples need to be taken at the same time as the NP swabs. If taking both samples is not feasible, the NP should be given priority. Collected samples need to be sent to the central lab to explore quantification of viral load. Sequencing might be performed upon request of the virologist to determine mutations in the viral genome.

Only one sample should be collected if the NP sample for detection and the NP sample for quantification are collected on the same day. This sample should be aliquoted and the remaining aliquots of the NP samples should be stored and sent to the central lab for quantification of SARS-CoV-2.

For each participant, NP sampling should be done at approximately the same time (\pm 4 hours) on each sampling day and from the same nostril.

Leftover NP swabs and endotracheal samples may be used for exploratory biomarker analyses.

If viral RNA is detected in nasopharyngeal samples at day of discharge, all possible efforts will be made to follow-up subjects and collect samples every 7 days until viral RNA is negative, considering the current pandemic and related logistical challenges. If possible, home visits by a healthcare professional may be conducted to collect samples during the follow-up period.

The frequency and timing of the assessments can be found in the [Schedule of Activities \(SoA\)](#). Details about sample collection, processing, and shipping will be provided in the laboratory manual.

Blood samples

In addition to NP swabs, plasma samples will be collected to assess SARS-CoV-2 viremia. Leftover serum samples may be used for exploratory biomarker analyses.

The frequency and timing of the assessments can be found in the [Schedule of Activities \(SoA\)](#). Details about sample collection, processing, and shipping will be provided in the laboratory manual.

Stool Samples (if feasible)

In addition to respiratory tract and plasma samples, stool samples will be collected to explore quantification of viral load of SARS-CoV-2 virus. The stool collections will only be collected if feasible for the site.

Collected samples need to be sent to the central lab. Leftover stool samples may be used for exploratory biomarker analyses.

The frequency and timing of the assessments can be found in the [Schedule of Activities \(SoA\)](#). Details about sample collection, processing, and shipping will be provided in the laboratory manual.

8.1.4. Supplemental Oxygen Use

Supplemental oxygen/percentage of inspired oxygen (FiO₂) use (if any) will be measured to monitor the patient's status regarding gas exchange as applicable. The following will be recorded:

- Oxygen delivery device (eg, nasal cannula, simple face mask, nonrebreather mask, high flow nasal cannula, non-invasive ventilation, invasive mechanical ventilation, extracorporeal life support, etc)
- Oxygen flow rate in liters/min
- Record FiO₂ and SpO₂ data 4 times per day, and at any time of arterial blood gas measurements. Record values that are sustained for at least 1 hour.
- If a patient is using more than one device (eg, extracorporeal life support and invasive ventilation), the worst value of FiO₂ (and the corresponding SpO₂ -and PaO₂ if available-) on the highest level of intervention will be recorded. The worst (highest) value of FiO₂ (and the corresponding SpO₂ -and PaO₂ if available-) on each device will also be recorded.
- If a patient does not need oxygen supplementation, this should also be recorded.

The frequency and timing of the assessment can be found in the [Schedule of Activities \(SoA\)](#).

Note: The use of CPAP at home for obstructive sleep apnea syndrome will not be reported as a need of oxygen supplementation information. Only the information on oxygen supplementation that is COVID-19 related is to be reported.

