8.1.1 Six-point Ordinal Clinical Recovery Scale	
Edits are made to the 6-point ordinal clinical recovery scale to clarify that:
 
 For participants not hospitalized (category 1), a distinction will be made between participants discharged and in need of (score 1.2) or not in need of (score 1.1) oxygen supplementation as indicated by the investigator on the discharge questionnaire. Regardless of the device used: 
 Hospitalized participants with a FiO₂ below 50% corresponds to a category 3. Hospitalized participants with a FiO₂ of 50% or higher corresponds to a category 4. 	
Clarification on category 1.
 
Clarifications on categories 3 and 4 to make category 3 fully consistent with category 4, which is using the FiO₂ as a threshold and making the allocation to category 3 or 4 independent of the device used.

8.1.4 Supplemental Oxygen Use	Clarify that the use of CPAP at home for obstructive sleep apnea syndrome will not be reported as a need for supplemental oxygen information.	Clarification.
10.1 Appendix 1: Abbreviations and Definitions	Definitions of critical and severe COVID-19 disease have been added to the definitions of terms.	Clarification.
1.1 Synopsis 1.3 Schedule of Activities (SoA) 4.1 Overall Design 10.2 Appendix 2: Clinical Laboratory Tests 10.3 Appendix 3: Clinical and Laboratory Assessments Described per Day	Minor rewording. Corrections for respiratory and vital signs assessments to be performed once weekly after Day 28 if still hospitalized.	Clarification.
Throughout the protocol	Minor formatting and minor updates made.	Minor errors were noted.

TABLE OF CONTENTS

PROTOCOL AMENDMENT SUMMARY OF CHANGES TABLE	2
TABLE OF CONTENTS	5
LIST OF IN-TEXT TABLES AND FIGURES	7
1. PROTOCOL SUMMARY	8
1.1. Synopsis.....	8
1.2. Schema	17
1.3. Schedule of Activities (SoA).....	18
2. INTRODUCTION.....	25
2.1. Study Rationale	25
2.1.1. Background.....	25
2.2. Dose Rationale.....	37
2.3. Benefit-Risk Assessment	38
2.3.1. Risks for Study Participation.....	38
2.3.2. Benefits for Study Participation	38
2.3.3. Benefit-Risk Assessment for Study Participation	39
3. OBJECTIVES AND ENDPOINTS	40
4. STUDY DESIGN	42
4.1. Overall Design.....	42
4.2. Scientific Rationale for Study Design.....	43
4.2.1. Study-Specific Ethical Design Considerations	45
4.3. Justification for Dose.....	46
4.4. End of Study Definition.....	46
5. STUDY POPULATION	46
5.1. Inclusion Criteria	47

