2.3. Benefit-Risk Assessment

2.3.1. Risks for Study Participation

Potential risks for participants treated with sirukumab single IV dose are the occurrence of infusion reactions, hypersensitivity, serious infections, liver enzymes increase, and neutropenia/thrombocytopenia (see Section 8.3.6). Of these the most significant risks relate to the complications associated with immunosuppression, essentially bacterial, fungal and viral infections.

The following risk mitigations are in place:

- The study population will be under continuous monitoring in a hospital/intensive care setting.
- The protocol prevents patients with the most severe COVID-19 disease (eg, on invasive mechanical ventilation or veno-venous ECMO for >48 hours) and pre-existing comorbidities (including non-COVID-19-related active infections, severe COPD, steroid dependency, being on renal replacement therapy, chronic liver disease, malignancy), patients ≥85 years of age, from participating.
- To further protect the participants from the immunomodulatory effects of sirukumab that may predispose them to infections, the investigators are referred to the local guidelines for the concomitant use of antibacterials and/or agents that are intended to inhibit SARS-CoV-2 viral activity for management of community acquired pneumonia, COVID-19 pneumonia, or secondary infections. Open-label or off-label use of agents that are intended to inhibit SARS-CoV-2 viral activity, with demonstrated in-vitro effect, as mentioned in the CDC guidelines on Therapeutic Options for patients with COVID-19 are permitted in the study.⁶

The co-administration of convalescent plasma introduces an additional protein load of 2.4 to 8 g/L.^{25,35} This may be a concern in patients with renal impairment, however it is noted that the following risk mitigations are in place:

- The exclusion criterion 10 prevents patients with an estimated glomerular filtration rate (eGFR) ≤30 mL/min/1.73 m² or requiring renal replacement therapy from participating.
- The study population will be under continuous monitoring in a hospital/intensive care setting.

The inclusion of a Data Monitoring Committee (DMC) will ensure oversight of patient safety (see Section 10.4.6, Committee Structure).

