5.2. Exclusion Criteria

Any potential participant who meets any of the following criteria will be excluded from participating in the study:

1. Criterion modified per Amendment 2
 - 1.1 On invasive mechanical ventilation or on veno-venous ECMO for >48 hours at time of screening.
2. Meets local or global criteria to not receive mechanical ventilation or has designated themselves as DNR per a living will.
3. Criterion modified per Amendment 2
 - 3.1 Received an investigational intervention (including investigational vaccines) or used an invasive investigational medical device within 30 days before the planned dose of study intervention.

Note: the investigator must ensure that the participant is not enrolled in another COVID-19 study with an investigational intervention (apart from the exception specified below) prior to completion of Day 28 of the current study.

Exceptions: Participation in a single arm study, a non-blinded controlled study, expanded access, compassionate use program or any other program that is not a blinded study is allowed if it is conducted with one of the following:

- agents with demonstrated in vitro-effect against SARS-CoV-2, as mentioned in the CDC guidelines.⁶
- convalescent plasma.

4. Criterion modified per Amendment 2

4.1 Current confirmed or high suspicion for pulmonary embolus, hemodynamic significant pericardial effusion, myocarditis, or Class 3 or 4 congestive heart failure as defined by the New York Heart Association Functional Classification (Section 10.9, Appendix 9)

AND/OR

Current evidence of active cardiac ischemia.

5. Criterion modified per Amendment 1

5.1 Criterion modified per Amendment 2

5.2 Currently active clinically significant (eg, causing hemodynamic instability and/or causing hypoxemia) and uncontrolled arrhythmia.

6. Liver function impairment defined as Child Pugh Class B/C based on medical history.

7. Has congenital bleeding diathesis based on medical history.

8. Criterion modified per Amendment 2

8.1 Has a history of chronic respiratory condition (ie, asthma, chronic obstructive pulmonary disease [COPD], cystic fibrosis, fibrotic lung disease) that requires home oxygen supplementation, supportive non-invasive ventilation, or is status/post lung volume reduction surgery (LVRS)

Exception: Participants with sleep apnea using supportive non-invasive ventilation (continuous positive airway pressure [CPAP]) at screening may be included.

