8.1.1. Six-point Ordinal Clinical Recovery Scale

The 6-point ordinal clinical recovery scale provides 6 mutually exclusive conditions ordered from best to worst, and the score reflects the participant's worst situation on the day assessed. The sponsor will assign the ordinal scale category based on the assessment of the participant's clinical status by the investigator. The ordinal clinical recovery scale categories are defined below.

Ordinal Clinical Recovery Scale (and Definitions)^a

1. Not hospitalized^b

Any of the following:

- Discharged from the hospital the day of assessment
- Hospitalized at the day of assessment but ready for discharge on the day of assessment, as judged by the investigator (eg, if still hospitalized in case of lack of bed availability in a skilled nursing facility, lack of social support at home).

2. Hospitalization, not requiring supplemental oxygen

^a Alternate care settings delivering care which would normally be delivered in a hospital setting will be categorized as hospitalized.

If a participant was discharged from the hospital “Against Medical Advice” on the day prior to the day of assessment, the participant will be categorized per the definitions above in the category the participant was in at the moment of discharge “Against Medical Advice”. The hospital recovery scale category will be considered missing on subsequent days.

If a participant declines medically-indicated mechanical ventilation, the participant will be categorized according to the care they would otherwise have received on that day.

^b A distinction will be made between participants discharged and in need of (score 1.2) or not in need of (score 1.1) oxygen supplementation as indicated by the investigator on the discharge questionnaire. This distinction will not be made when calculating improvements on the CRS, for which score 1 will be used in both cases.

3. Hospitalized, requiring low flow supplemental oxygen

- Hospitalized on the day of assessment (including readmittance), and supplemental oxygen is required by the participant.

Requiring supplemental oxygen is defined by:

- Receiving supplemental oxygen for instance through a face mask or nasal cannula, at a $\text{FiO}_2 < 50\%$,^a and not being able to sustain a blood oxygen saturation of $>93\%$ when breathing room air.

OR

- Not receiving supplemental oxygen and having a blood oxygen saturation of $\leq 93\%$ sustained for 5 minutes.

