4. Hospitalized, on non-invasive ventilation, nonrebreather mask, or high flow oxygen device

- On supplemental oxygen, on one of the above modalities, with a FiO_2 (worst of the day) of 50% ^a or higher unless they satisfy a higher category (eg, on invasive mechanical ventilation). Note, the use of other devices may fit with category 4 if the FiO_2 is 50% ^a or higher.

5. Hospitalized, on invasive mechanical ventilation or ECMO

- Any oxygen support requiring intubation or extracorporeal oxygenation.
- Invasive mechanical ventilation is used at any time on the day of assessment.

6. Death

- Participant died at any time on the day of assessment or earlier (all-cause mortality).

In addition, the site will be asked whether or not they are working under (a) restricted material resources for supplemental oxygenation/ventilation and/or (b) changes in hospital discharge policies.

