3. If a subject is hospitalized, but is ‘ready for discharge’ according to the investigator, the subject will be considered hospitalized up to and including the first day on which the subject was considered ready for discharge. The subject will be considered “Not hospitalized” from the day after until day 28/trial discharge (unless the status changes back to “not ready for discharge”).
4. If a subject is discharged, but is ‘not ready for discharge’ according to the investigator, the subject will be considered hospitalized up and including 1 day after the day of discharge or until trial discontinuation. The subject will be categorized in the category the subject was in at the moment of discharge. The subject will be considered non hospitalized from 2 days after the day of discharge onwards until day 28/trial discontinuation.
5. If a subject is discharged from the hospital, the day of discharge will be considered as “hospitalized”. The subject will be categorized in the category the subject was in at the moment of discharge. After this day, the subject will be considered “Not hospitalized” until day 28/trial discontinuation.

CRS Derivation

The Ordinal Clinical Recovery Scale can be derived from Baseline up to and including Day 28, or until trial discontinuation. Participant who died before day 28 (before or after hospital discharge, but before trial discontinuation) will be considered to continue the trial up to and including day 28.

For the derivation, we will start with the highest score.

If the subject didn't fall into this category, we will check for the next highest score.

- **Score 6:** Based on the status of the participant on the day of the assessment (based on the date of death).

Based on Type of Oxygen Supplementation page:

- **Score 5:** At least one of the following scores is ticked:
 - IMV
 - Extra Corporeal Membrane Oxygenation
 - The question “Is the subject on Mechanical Ventilation” is answered “No”, and the question “From a Medical Perspective, should the patient be on IMV?” is answered “Yes”. (on Subject Status Form)*
- * To comply with the note: “*If a participant declines medically-indicated mechanical ventilation, the participant will be categorized according to the care they would otherwise have received on that day*”
- **Score 4:**
 - Subject is on supplemental oxygen and the FiO2 is $\geq 50\%$.
- **Score 3:**
 - Hospitalized & **requiring low flow supplemental oxygen, defined as**

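### Section 8.1.4 limits oxygen reporting to COVID-19-related use, which conflicts with the cause-neutral recovery scale and, if followed literally, can create or preserve a false improvement on the primary endpoint

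*Protocol*

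**What the plan says.** **Recording rule.** Protocol 8.1.4 asks for delivery device, flow, FiO2 and SpO2. Its device list includes invasive ventilation and extracorporeal life support. It closes with a two-sentence note: "The use of CPAP at home for obstructive sleep apnea syndrome will not be reported as a need of oxygen supplementation information", followed by "Only the information on oxygen supplementation that is COVID-19 related is to be reported". The second sentence is not limited to CPAP.

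**Scale.** Protocol 8.1.1 scores the participant's "worst situation on the day assessed". Category 5 applies when "Invasive mechanical ventilation is used at any time on the day of assessment", category 4 is set by FiO2 of 50% or more, and category 6 is death from any cause. Footnote j of the Schedule of Activities (Section 1.3) asks for the oxygen data with no condition on cause.

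**Derivation.** SAP 5.2.1 repeats the categories without reference to cause. SAP Attachment 3 introduces its oxygen rules with "Based on Type of Oxygen Supplementation page". Categories 4 and 3 also rest on reported oxygen, FiO2 and SpO2, and category 2 is what remains for a hospitalized participant. SAP 5.2.1 treats an improvement as sustained unless its loss is documented by Day 28 or discontinuation.

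**Pre-existing support.** Exclusion criterion 8.1 removes chronic respiratory conditions that need home oxygen, but "Participants with sleep apnea using supportive non-invasive ventilation (continuous positive airway pressure [CPAP]) at screening may be included". Section 5.1, in describing severe disease, allows that some participants have an oxygen requirement that predates COVID-19.

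**The concern.** Sites hold two instructions for the data behind the primary endpoint. One scores the worst support of the day whatever its cause. The other asks for an attribution first, in participants who all have COVID-19, and gives no rule for making it. Oxygen or ventilation for a secondary pneumonia, sepsis or an embolism is where the two part.

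The direction matters because Protocol 2.3.1 says of the potential risks of sirukumab: "Of these the most significant risks relate to the complications associated with immunosuppression, essentially bacterial, fungal and viral infections". If such complications are more frequent on sirukumab and their support goes unrecorded, the efficacy scale would lean towards the drug. The same data feed Day 28 improvement, worsening on the scale (also a monitoring committee criterion in Section 10.4.6), time to end of oxygen, and ventilation-free days.

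**Working it through.** **1. What an omitted entry does to the score.** Take a hospitalized participant on support that the site has left off the oxygen page. The derived category follows SAP 5.2.1 and Attachment 3.

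| On file for the day | Category | From baseline 4 | From baseline 5 |
|---|---|---|---|
| Off oxygen, all SpO2 above 93% | 2 | 2 better | 3 better |
| Off oxygen, lowest SpO2 93% or less | 3 | 1 better | 2 better |
| Entry treated as incomplete | missing | no new gain; earlier gain kept | no new gain; earlier gain kept |
| *Correctly recorded: FiO2 50% or more* | 4 | 0 | 1 better |
| *Correctly recorded: invasive ventilation* | 5 | 1 worse | 0 |

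The primary endpoint needs a gain of 2. The first row reaches it from either baseline and the second only from baseline 5. The third creates no improvement but leaves an earlier one undisturbed, because no loss is documented. The plainest case is a participant who improves and then needs oxygen again for a secondary infection.

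Three provisions bear on whether the error would be caught:
- Section 8.1.5 has SpO2 measured on support in ventilated participants, so it can exceed 93%. For other oxygen, Appendix 10 asks for a room-air reading, which makes the second row more likely.
- Attachment 3 uses the ventilation question on the Subject Status Form only when the answer is no and the participant should have been ventilated. It does not recover an unreported ventilated day.
- The CRS (As observed) scale in SAP 5.4.1 reads the same oxygen page.

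**2. The plan's own figures.** Inputs from Protocol 9.2: 74 vs 37 participants; lognormal survivor times with medians 16.8 and 28 days and SD of log 0.9; mortality 20% vs 40%; deaths censored at Day 28; two-sided 5% log-rank test.
- Control improvement by Day 28: 0.6 × Φ(0) = 30.0% (stated 30%).
- Sirukumab: 0.8 × Φ(ln(28/16.8)/0.9) = 0.8 × Φ(0.568) = 57.2% (targeted 55%).
- Simulated power, unstratified: 82% with whole-day times and 81% with continuous times (stated at least 80%).

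The model reproduces the plan, so it can be used for illustration.

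**3. Illustration: false wins.** Assume no true effect (40% mortality and median 28 days in both arms). Then 60% survive, 30% improve and 30% are surviving non-improvers. Assume that a share of the last group is scored as improved at some day from 7 to 28 because support went unreported. Recorded improvement is 30% + share × 30%; for example, a 20% share gives 36%. With 2,500 trials per scenario and control shares of 0, 5, 10 and 20%:

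| Share on sirukumab minus control | Significant result for sirukumab (nominal 2.5%) |
|---|---|
| 0 points | 1.8–2.2% |
| 5 points | 2.2–4.0% |
| 10 points | 4.1–4.9% |
| 20 points | 6.8–8.2% |
| 30 points | 11.1–14.1% |

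Simulation error is about 0.3 to 0.7 percentage points. Equal omission in the two arms does not inflate false wins.

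**4. Illustration: a masked deficit.** Suppose 10% of sirukumab and 3% of control participants remain on support for another cause to Day 28, with no other drug effect and every such case omitted.
- If all of them would otherwise have improved, the true deficit is 10 − 3 = 7 points and about 0 is recorded. The chance of a significant result for harm falls from about 15–18% to 3–4%.
- If they are spread over all participants independently, the deficit is (0.10 − 0.03) × 30 = 2.1 points. The chance of detecting it is about 5% even with full recording, against about 3% under the null.

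The answer therefore depends heavily on where the cases are assumed to fall.

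**The case against.** The strongest reply is that the sentence closes a note about home CPAP. The summary of changes for Amendment 5 describes the edit only in those terms: "Clarify that the use of CPAP at home for obstructive sleep apnea syndrome will not be reported as a need for supplemental oxygen information". On that reading the scale definitions govern, and a site would have to call new oxygen in critical COVID-19 unrelated to COVID-19 and then leave it off the form. This stands as evidence of intent. It does not put a limit into the sentence that sites are asked to follow.

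An omitted entry also need not score as improvement. Section 8.1.4 wants absence of oxygen need recorded positively, Attachment 3 names incomplete oxygen information as a cause of a missing score, and a low room-air SpO2 gives category 3. These points stand and narrow the mechanism. They do not close it, as the table shows.

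A reader might go further and infer that the drug's main harm is hidden. The documents do not support that. All adverse events are reported (8.3.1), any new infection is an adverse event of special interest (Section 1.3), and events that prolong hospitalization are serious (10.5.5). Severe or life-threatening infection and all-cause mortality are endpoints (Section 3). Participants who die by Day 28 are never counted as improved (SAP 5.2.3).

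A reader might also infer that the general sentence has no legitimate use, given exclusion 8.1. That criterion covers only chronic respiratory conditions, while Section 5.1 contemplates a pre-COVID oxygen requirement, so some exception for prior use is reasonable.

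**Conclusion.** The conflict is real: a recording rule restricted by cause feeds a scale that is not. Followed literally, it can produce or preserve a false improvement on the primary endpoint, and the alternative scale would not reveal it.

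The documents do not show that any site applied it this way, nor that participants with complications are scored as improved as a matter of rule. Bias towards sirukumab needs three things together: literal application, attribution to a cause other than COVID-19, and more such cases on sirukumab. The documents give no rate for any of them. The lupus nephritis infection figures in Section 2.1.1 come from repeat 10 mg/kg dosing, with all serious infections after at least four doses, and cannot supply the rate for a single 5 mg/kg dose.

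The size is therefore unknown. The simulated figures rest on assumed shares, and the masked-deficit figures also assume that every affected case is omitted. The contradiction and the unguided attribution need correcting whatever the size, and the correction is cheap.

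**What to change.** Reconcile 8.1.4 with 8.1.1. Suggested wording: *Pre-existing home CPAP, or home oxygen at the pre-COVID level, is not reported as a need for supplemental oxygen. All other supplemental oxygen and ventilatory support from randomization to Day 28 is recorded, whatever its cause.* Align the eCRF completion guidelines with it.

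Before database lock, ask sites whether any support was left out as not COVID-19 related, using serious adverse event and concomitant-therapy records to target the queries. Then re-derive the recovery scale and the endpoints that depend on it. The summary of changes lists the CPAP note under Amendment 5, and the critical population includes participants enrolled before and after that amendment, so the queries should cover both periods.

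The cost is one protocol sentence, a matching guideline edit and a small query round. No new assessments are needed.
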